6.4 Study Discontinuation by IRB or Sponsor

The IRB may choose to discontinue the study at any center(s) for which they granted approval if the:

- The research study is not conducted in accordance with the IRB requirements.
- The research study indicates unexpected serious harm to Subjects.

The Sponsor may choose to discontinue the study should the Sponsor discover additional information during the study that may cause harm to subject safety.

If the study is terminated prematurely or suspended, the Sponsor will promptly inform all clinical Investigators of the termination or suspension and the reason(s) for this. The IRB/EC will also be informed, either by the Sponsor or Investigator if a local IRB/EC is utilized, promptly and provided with the reasons(s) for the termination. If applicable, regulatory authorities will be informed.

DWF-C0001-001 CONFIDENTIAL Page 21 of 44

6.5 Study Schedule

6.5.1 Schedule of Assessments

Schedule of Assessments					
Assessments	Screening ¹	Procedure ¹	Follow-Up ¹		
Informed Consent	х				
Demographics	Х				
Relevant Medical History	Х				
Physical Exam ◆	Х				
SOC TCD Bubble Study Exam ◆		O ⁴			
NB-IS TCD Bubble Study Exam		X ²			
Transthoracic Echocardiograph (TTE) Bubble Study ◆		X ³			
Transesophageal Echocardiograph (TEE) ◆		O ⁴ / X ⁸			
PFO Closure Decision ◆			X ⁵		
Classification of Potential Causative Mechanism in PFO–Associated Stroke ⁷ ♦			Х		
PFO Closure Procedure ◆			O _e		
Device-Related Adverse Events		Х			
Procedure-Related Adverse Events		х			
Concomitant Medications	х	х			
Device Deficiencies		Х			

- ♦ Standard of Care X = Required O = Optional, if performed
- 1. Screening, Procedure, and Follow-Up Visits can occur on the same day
- 2. NB-IS TCD performed with contrast agent of 9 ml bacteriostatic saline with 1 ml air mixed 10 times. Performed at Rest AND with VM 60 sec recordings each in supine positions AND with HOB raised to 45 degrees.
- 3. TTE can be performed within ±30 days of informed consent per SOC.
- 4. SOC TCD and TEE results collected if performed as applicable per standard of care.
- 5. PFO closure decision collected post diagnostic imaging procedures.
- 6. PFO closure procedure data collected within 60 days post diagnostic workup, if performed
- 8. SOC TTE or TEE will be required after the first 150 TTE subjects are enrolled and can be performed within ±30 days of informed consent per SOC.

6.6 Scanning/Data Acquisition

The User Manual provided for the device details, in specific steps, the actions to be executed with the device for scanning/data acquisition. A general overview is provided below.

6.7 NeuralBot Investigational System (NB-IS) Scanning Technique

The NB-IS TCD scanning session will consist of an initial set-up and signal search (up to 20 minutes). During this time, the system will search for CBFV signals at depths between 40-65 mm. Once the signal is acquired, the system can monitor the signal for up to 1 hour. In this study, once

the MCA signal has been acquired unilaterally or bilaterally, subjects will be monitored for up to 20 minutes during the delivery of the contrast agent at Rest and with Valsalva Maneuver.

The head cradle of the NeuralBot Investigational System is positioned underneath the subject's head and secured to a fixed location (bed, chair, or gurney). The user will affix two registration dots on each side of subject's temples. The subject's head is then positioned into the head cradle. The TCD modules are aligned to the head such that the probes are in contact with the subject's temples (temporal window). The user will register the Headmount to the subject's specific head shape and size. The user will apply gel to improve signal quality. The NeuralBot Investigational System will collect data and indicate to the user the scan status.

Subjects will be evaluated during the scanning period per ALARA ("As Low As Reasonably Achievable") criteria. Scanning may not violate ALARA levels and will be immediately terminated if ALARA criteria reached during a scanning session.

6.8 ALARA Considerations

ALARA Considerations: "As Low As Reasonably Achievable – ALARA" principle for ultrasound to reduce the amount of total exposure to the subject without compromising exam quality.

Diagnostic ultrasound, including TCD, has been used clinically and in research for decades. In addition to the FDA guidance, there are several groups including the American Institute of Ultrasound in Medicine (AIUM), British Medical Ultrasound Society (BMUS), and the World Federation for Ultrasound in Medicine and Biology (WFUMB) that make recommendations on ultrasound safety for both fetal and non-fetal applications. These groups have focused on several areas of ultrasound safety including Thermal Index (TIC).

The FDA specifically references the AIUM for the ALARA recommendations for TIC and corresponding scan durations in the new guidance released in October 2017. Table 1 shows the recommended scan duration for a given TIC range. The ALARA recommendations are based on the TIC output by the device (which is displayed on the Lucid M1 System device at all times). TIC is defined as:

TIC – the thermal index for applications in which the ultrasound beam passes through bone near beam entrance into the body.

Thermal Index (TIC)	Recommended Duration (minutes)
>6.0	0
5.0-6.0	0.25
4.0-5.0	<1
3.0-4.0	<4
2.5-3.0	<15
2.0-2.5	<60
1.5-2.0	<120
<1.5	No Limit

DWF-C0001-001 CONFIDENTIAL Page 23 of 44

Table 1 - Recommended maximum exposure duration and TIC ranges (except the eyes which are not evaluated in this protocol)

If a subject meets ALARA criteria at any time during a scanning session, the scan will be discontinued.

6.9 Standard of Care Procedures

Most procedures completed as part of this study are considered standard practice and include relevant medical and medication history, physical exam, SOC transcranial Doppler ultrasound (TCD) bubble study, transthoracic echocardiography (TTE) bubble study, transesophageal echocardiography (TEE) bubble study, and PFO closure (status), if performed.

This study is incorporating the use of NB-IS TCD bubble study in conjunction with standard of care procedures.

6.10 Study-Specific Procedures

The procedures that are study-specific and not part of standard of care for diagnosis and treatment of RLS and PFO include the use of the NB-IS TCD System bubble study.

6.11 Screening Procedures

The following data will be collected, and assessments performed after obtaining informed consent from eligible subjects and prior to the NB-IS TCD procedure.

- Informed Consent
- Subject Demographics
- Relevant Medical History
- Physical Exam (SOC)
- Relevant Concomitant Medications

6.12 Procedure –NB-IS TCD Scanning Session

The NB-IS TCD bubble study can be performed during the same session as SOC TCD bubble study is performed and preferably before TTE and TEE (if applicable) bubble studies are performed. If a TTE bubble study is performed before TCD bubble study, the SOC TCD operator will ensure he/she are blinded to the results of the TTE prior to performing TCD. The NB-IS TCD operator will perform scanning sessions as follows:

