2.5 Potential Risks and Benefits

TCD ultrasonography is a safe, non-invasive, and reproducible technique that allows the assessment of cerebral blood flow (CBF) in a person. TCD data collection relies on the level of experience of a TCD technologist to acquire an accurate and high-quality signal from the intracranial vessel(s) of interest, thus per user, the data quality is variable⁹. NovaSignal has developed the NeuralBot Investigational System (NB-IS) to assist in the TCD data collection such that consistent high-quality data may be obtained independent of the experience of the user.

NovaSignal will collect safety and technical feasibility data regarding the use of TCD ultrasound via the NeuralBot Investigational System (NB-IS) device in humans. Data collected during this study is for research purposes only. No treatment or healthcare decisions will be made based on study measurements collected in this study.

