6.12.5 Transthoracic Echocardiography Procedure (TTE) per SOC

The TTE bubble study can be performed per standard of care within ±30 days of informed consent.

The following data points will be collected for the TTE procedure:

- Transthoracic Echocardiography (TTE) local results (SOC)
 - Date/Time of TTE bubble study
 - TTE Start/stop times with and without VM (as applicable)
 - Saline/Air Injection(s) Start/Stop time(s) with and without VM (as applicable)
 - Local Positive/Negative results for RLS/PFO
 - Local Bubble Count (as applicable)
 - Local TTE grading (as applicable)

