11.4 Imaging Core Lab Analysis

All de-identified imaging data will be sent to a core laboratory which will provide independent quantitative and qualitative assessment of all NB-IS TCD and SOC TCD, TTE, and TEE bubble study data. They will be blinded to the study and local diagnostic report data and provide independent review. The Core Lab interpretations will supersede all local interpretations and will be applied to all study endpoint analyses as applicable.

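### NB-IS is preferably done before echo, but no rule keeps the TTE or TEE operator unaware of what it showed, so echo acquisition could depend on the index test

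*Combined protocol and SAP*

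**What the plan says.** Section 6.12 of the combined protocol and SAP places the NB-IS bubble study "preferably before TTE and TEE (if applicable) bubble studies are performed". This is a preference, not a requirement. If TTE happens to come first, "the SOC TCD operator will ensure he/she are blinded to the results of the TTE prior to performing TCD". That is the only operator-level blinding in the document. Sections 6.12.5 (TTE) and 6.12.6 (TEE) contain none.

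On timing and conduct of the comparator, Section 6.12.5 says "The TTE bubble study can be performed per standard of care within ±30 days of informed consent". Its data items include "TTE Start/stop times with and without VM (as applicable" and, for the contrast, "Saline/Air Injection(s) Start/Stop time(s) with and without VM (as applicable". Section 6.12.6 is tighter for TEE: a referred subject has the bubble study at rest and with Valsalva, along the lines of the NB-IS examination.

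On reading, Section 11.4 says of the core laboratory: "They will be blinded to the study and local diagnostic report data and provide independent review". It adds: "The Core Lab interpretations will supersede all local interpretations and will be applied to all study endpoint analyses as applicable".

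On use of the NB-IS data, Section 2.5 says "No treatment or healthcare decisions will be made based on study measurements collected in this study", and Section 3.3 says that the device is not used for diagnosis in this study.

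**The concern.** The primary endpoint sets NB-IS detection against TTE detection in the same subjects, so the TTE result is half of the contrast. In the order that the protocol prefers, the NB-IS scan is finished before the echo begins. Bubbles can be seen during that scan: Section 6.12.4 has staff wait between injections until they have cleared, and Section 3.1 says the TCD system can give an emboli count. The schedule of assessments lets all visits fall on one day.

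An echo operator who knows that bubbles were seen may repeat an injection, coach the Valsalva harder or look longer. One who knows that none were seen may stop sooner. Section 6.12 already accepts that knowing one test can affect how the next is performed, but guards against it only in the non-preferred order and only for SOC TCD.

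At stake are the NB-IS versus TTE difference, the secondary accuracy measures against TTE, and, to a lesser degree, agreement with TEE. An acquisition that was altered cannot be restored afterwards by a blinded reader.

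**Working it through.** **1. Reproduce the plan's figure.** Inputs from Section 11.6: sensitivities 0.90 (TCD) and 0.50 (TTE), prevalence 0.30, discordant proportion 0.50, two-sided McNemar test at 0.05, N = 100.

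- Shunt-positive subjects: 100 × 0.30 = 30.
- Let a = P(NB-IS+, TTE−) and b = P(NB-IS−, TTE+) among them. Then a + b = 0.50 and a − b = 0.90 − 0.50 = 0.40, so a = 0.45 and b = 0.05.
- Exact McNemar power, summed over the number of discordant pairs, is 0.89995. This equals the tabulated value. The rows from N = 20 to N = 150 also match to five decimals.

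The planned power is therefore not in dispute. The question is what happens to its inputs if echo effort depends on NB-IS.

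**2. More effort after a positive NB-IS.** Assume that a fraction f of the NB-IS-positive shunts that TTE would have missed is recovered. The value of f is an assumption; the documents give none. Then

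- TTE sensitivity = 0.50 + 0.45f
- expected difference = 0.45(1 − f) − 0.05

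| f | TTE sensitivity | Difference | Power, 30 positives | Power, 43 positives (144 × 0.30) |
|---|---|---|---|---|
| 0 | 0.500 | 0.400 | 0.900 | 0.981 |
| 0.1 | 0.545 | 0.355 | 0.832 | 0.957 |
| 0.2 | 0.590 | 0.310 | 0.738 | 0.908 |
| 0.3 | 0.635 | 0.265 | 0.616 | 0.820 |

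For scale, TTE detection among NB-IS-positive shunts starts at (0.90 − 0.45)/0.90 = 50%. With f = 0.2 it becomes (0.45 + 0.09)/0.90 = 60%.

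If only a share s of subjects has NB-IS first and the observation becomes known, f is replaced by s × f. For example, f = 0.2 in half the subjects gives the f = 0.1 row.

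**3. Less effort after a negative NB-IS.** Assume that a fraction g of the NB-IS-negative, TTE-positive shunts is lost. The expected difference is 0.45 − 0.05(1 − g).

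- g = 0.5: difference 0.425, power with 30 positives 0.967.
- g = 1: difference 0.450, power 0.999.

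This moves the result in the device's favour. The same behaviour at TEE would raise apparent agreement.

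**4. Safeguards set against the gap.** Core-lab blinding acts after acquisition. Sections 2.5 and 3.3 restrict what NB-IS data are used for, not who may see the screen. The rule in Section 6.12 covers one operator in one order. None of them reaches the echo operator in the preferred order.

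**The case against.** The strongest reply is that the route is narrow, and much of that stands.

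- **No formal NB-IS result exists at the site.** Sections 6.12.3, 6.12.5 and 6.12.6 each ask for a local positive or negative result. Section 6.12.4 asks for none for NB-IS, and the synopsis limits local Spencer and ICC grades to SOC TCD. A reader might infer that NB-IS findings are passed to the echo team. The documents do not say so. What remains is informal leakage from the scan.
- **Acquisition is partly fixed.** The entry criteria require a scheduled agitated-saline study, and Section 2.2 describes all these procedures as involving injection and Valsalva. The wording about applicability in Section 6.12.5 sits on data fields and does not instruct the operator. TEE is steered to resemble the NB-IS examination. The opening is therefore mainly at TTE.
- **Order is only preferred.** TTE may come first, so the exposed share of subjects is unknown.
- **The bias is conservative.** This does not stand. It holds for step 2 above but not for step 3, and the documents do not say which would prevail.

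Two stronger readings should be resisted. One is that success criterion (i) in Section 11.5 would be missed. The shift is assumed, and the criterion does not say whether 40% is absolute or relative: at f = 0.2 the relative increase is 0.90/0.59 − 1 = 53%. On the meta-analysis values in Section 11.6 (96.1% and 45.1%), a 10-point rise in TTE detection among TCD positives leaves 96.1 − (45.1 + 9.6) = 41.4 points.

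The other is that predictive value against TEE would be greatly inflated. That would need an unbiased TEE sensitivity well below the 95% in Section 2.3. Starting from 95%, little room for added detection remains.

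**Conclusion.** The gap is real and specific. In the order the protocol prefers, no rule prevents the acquisition of the comparator from depending on the index test, and blinded reading cannot repair that. It bears mainly on TTE, only in subjects scanned by NB-IS first, and only through informal knowledge of the scan.

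Its size and direction cannot be derived from the documents. Under the assumption that 10% to 30% of TTE-missed, NB-IS-positive shunts are recovered in all subjects, the expected difference falls from 40 to between 35.5 and 26.5 points. Power with 30 shunt-positive subjects falls from 0.90 to between 0.83 and 0.62; with 43 it falls from 0.98 to between 0.96 and 0.82. Slackened effort after a negative NB-IS would instead raise the difference to at most 45 points on the same inputs. These are illustrations, not estimates.

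A reader might go further and conclude that the trial is invalid or bound to fail its target; nothing in the documents supports that. The point should be acted on because prevention is cheap and later repair is impossible.

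**What to change.** Add to Section 6.12 that NB-IS observations and, where clinical care allows, SOC TCD observations are not disclosed to the TTE or TEE operator or the local echo reader until the echo images have been acquired and the local read entered. SOC TCD needs to be included because Section 6.12.3 prefers it in the same session, before NB-IS, with a local result and grades. Masking NB-IS alone would leave much the same information open.

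Add one yes/no eCRF item recording whether masking held.

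Keep all pairs in the primary analysis. Report results by test order, and with unmasked pairs excluded, as sensitivity analyses only. Disclosure may be likelier after a striking positive scan, so exclusion from the primary analysis could select on outcome. Test order needs no new data, because dates and times are already collected under Sections 6.12.3 to 6.12.6.

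The cost is one sentence, one eCRF item and two short tables. Sites must keep the TCD display and notes away from the echo team for a short time. The planned sample size and power are unchanged.

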4.1 Primary Efficacy Endpoint

 % detection of RLS/PFO with NB-IS TCD compared against standard of care Transthoracic Echocardiography (TTE)

4.2 Secondary Technical Efficacy Endpoints:

- % agreement for detection of RLS/PFO with NB-IS TCD vs SOC TCD
- % agreement for detection of RLS/PFO with NB-IS TCD vs Transesophageal Echocardiography (TEE)
- % agreement for detection of clinically significant shunts with NB-IS TCD vs TTE
- No window rate (including both unilateral and bilateral absent acoustic windows)
- Success rate of the NB-IS TCD
- Incidence of NB-IS device malfunctions

4.3 Exploratory Endpoints:

 Development of an automated algorithm for Spencer Logarithmic Scale¹⁰ and International Consensus Criteria grading of RLS¹¹

4.4 Primary Safety Endpoint:

Incidence of device-related serious adverse events.

4.5 Secondary Safety Endpoints:

Incidence of procedure-related adverse events related to agitated saline injection before and after VM (headache, allergic reactions, new onset neurological deficit, ischemic stroke, TIA or

DWF-C0001-001 CONFIDENTIAL Page 18 of 44

pulmonary embolism complicating agitated saline contrast injection, etc) will be closely monitored and prospectively collected¹².

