6.3 Screen Failures

Subject eligibility will be determined by the PI or study team based on their clinical assessment of the potential subject while the patient is undergoing standard of care assessments for a stroke in the hospital.

For this protocol, a single measurement is defined as a collection of data at a single depth on a single side of the head. A scan is defined as a set of measurements which occur during a single data collection session and can include multiple measurements. A bilateral scan refers to measurements which are collected on each side of the head.

Subjects will be measured with NB-IS TCD and the de-identified data will be reviewed to determine the quality of the data for analysis. Subjects are considered evaluable if their NB-IS TCD data is of adequate quality and a complete data set is acquired. An adequate, evaluable, and complete study is defined for the purposes of this protocol as successful acquisition of a unilateral signal at 40-65mm depth range recorded for the duration of the bubble study in the Resting position and with Valsalva Maneuver. If the scan quality is adequate, the subject study data (via eCRF) and imaging will be collected and the NB-IS TCD utilized for analysis of the study endpoints. If the scan quality is inadequate, all subject clinical and imaging data will not be included in the final analysis.

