6.12.4 NeuralBot Investigational System (NB-IS) TCD Procedure

The NB-IS TCD bubble study session will be conducted beginning in the supine position with the same IV line.

The NB-IS TCD operator will setup the study subject in the headmount of the NeuralBot Investigational System as per Section 6.7 NeuralBot Investigational System Scanning Technique. When the signal search has completed and the optimal signal has been identified unilaterally or bilaterally, the NB-IS device will continue monitoring the signal(s) for up to 20 minutes during the delivery of the contrast agent at Rest and with VM.

First, 10 mL of mixed contrast agent will be injected into the right antecubital vein while the subject is at rest and the MCA signal recorded for a period of 60 seconds. The subject will remain at rest for approximately 3 to 5 minutes or when bubbles have cleared.

Second, another 10 mL of contrast agent will be injected in the right antecubital vein and the VM performed mid-way through injection, sustained for ten seconds. The MCA signal will be recorded for a period of 60 seconds; characteristic MCA waveform morphology change and mean velocity decrease of at least 25% will serve as proof of adequate Valsalva effort¹⁷.

This procedure will be repeated with the study subject in the reclined position, with head of bed raised to 45 degrees where 10 mL contrast agent is injected when the subject is at rest and subsequently with a Valsalva Maneuver.

DWF-C0001-001 CONFIDENTIAL Page 25 of 44

The following data points will be collected for the NB-IS TCD scanning session:

- Date/Time of NB-IS TCD bubble study
- NB-IS TCD Operator (name)
- NB-IS TCD Scan information
 - o NB-IS TCD scan Start/Stop times with and without VM
 - Saline/Air Injection(s) Start/Stop time(s) with and without VM
 - Head inclination (degree)/subject positioning/location of the exam
- Relevant Concomitant Medications
- Device-Related Adverse Events (NB-IS)
- Procedure-related adverse events related to agitated saline injection before and after VM (headache, allergic reactions, new onset neurological deficit, ischemic stroke, TIA or pulmonary embolism complicating agitated saline contrast injection, etc) will be closely monitored and prospectively collected¹⁸.
- Device Deficiencies / Malfunctions / Technical Observations

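### The rule that blinds a TCD operator to an earlier TTE result names only the operator of the optional standard TCD and leaves out the operator of the robotic TCD, the index test of the primary endpoint

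*Combined protocol and SAP*

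**What the plan says.** Section 4.1 makes detection by NB-IS TCD against standard-of-care TTE the primary efficacy endpoint.

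Section 6.12 sets the order of the tests as a preference: the NB-IS study is done "preferably before TTE and TEE (if applicable) bubble studies are performed". For the case where TTE has come first, it adds that "the SOC TCD operator will ensure he/she are blinded to the results of the TTE prior to performing TCD". The next sentence turns to the index test without any blinding condition: "The NB-IS TCD operator will perform scanning sessions as follows".

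Section 6.12.5 gives the TTE window: "The TTE bubble study can be performed per standard of care within ±30 days of informed consent". Footnote 4 to the schedule in section 6.5.1 makes the exam named in the blinding rule optional: "SOC TCD and TEE results collected if performed as applicable per standard of care".

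Section 6.12.4 gives the NB-IS operator a hands-on role: "The NB-IS TCD operator will setup the study subject in the headmount of the NeuralBot Investigational System". Section 6.3 then decides who is analysed: "Subjects are considered evaluable if their NB-IS TCD data is of adequate quality and a complete data set is acquired". A subject whose scan fails that test leaves the final analysis.

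Section 11.4 has a core laboratory read all the imaging, blinded to study data and local reports. Its reads replace local reads for the endpoints.

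**The concern.** By writing the rule at all, the plan accepts that a known TTE result can colour how a TCD exam is carried out. It then protects a secondary comparator and leaves the index test of the primary comparison uncovered.

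The comparison is paired, so the result turns on the subjects in whom the two tests disagree. An operator who knows that TTE was negative may work harder, or less hard, to obtain a good recording. The same holds after a positive TTE. Either way, the tests would no longer be independent at the point of acquisition. The estimated difference in sensitivity could shift, and so could the set of subjects counted as evaluable. This cannot be repaired once the scans have been made.

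**Working it through.** No stated figure is in dispute, so the check sets the relevant sections side by side. For context, the power in section 11.6 reproduces. It assumes 100 × 0.30 = 30 subjects with a shunt and discordant cells of (0.500 + 0.400)/2 = 0.45 and (0.500 − 0.400)/2 = 0.05. An exact two-sided McNemar test at 0.05 then gives 0.8999, against the tabulated 0.89995. Blinding enters none of these inputs.

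**Step 1. Can the TTE result be known before the NB-IS scan?** Yes.
- Sections 6.1 and 6.11 place study procedures after consent, while section 6.12.5 lets TTE fall up to 30 days before consent. Every TTE in that earlier half of the window precedes NB-IS.
- A TTE after consent may also come first, because section 6.12 only prefers the opposite order.
- Section 6.12.2 gives instructions for contrast used at a TTE or TEE that precedes TCD, so the plan expects this order in some subjects.

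**Step 2. Whom does the rule cover?** Only the SOC TCD operator, and only for TTE. Sections 3.5, 6.7 and 6.12.4 add no blinding for the NB-IS operator. Where SOC TCD is not done, nobody is covered. The documents do not say how often that will be.

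**Step 3. What can a person still influence?**

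| Step in the NB-IS session | What the documents say | Room for influence |
|---|---|---|
| Headmount set-up, probe alignment, registration, gel | Done by the user (6.7, 6.12.4) | Yes |
| Signal search | Done by the device (3.2, 6.7) | Little |
| Valsalva training and coaching | Standardised module (3.5, 6.12.1); coach during the scan not named | Some |
| Valsalva timing and adequacy | Timing fixed; velocity fall of at least 25% required (6.12.4) | Little |
| Repeat of an inadequate Valsalva | No rule found | Yes |
| Contrast injection | Prescribed (6.12.2, 6.12.4); not assigned to the NB-IS operator | Some, through the injector |
| Evaluability decision | Later review of de-identified data against a written definition (6.3) | Indirect, through the quality of what was recorded |

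**Step 4. What does the core laboratory protect?** It protects the interpretation of each recording. It cannot restore a recording that was made with less care or never completed.

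**Step 5. Scale.** Under the planning values there are 30 × 0.500 = 15 expected discordant pairs. One changed NB-IS result among the 30 subjects with a shunt moves the sensitivity difference by 1/30 = 3.3 percentage points. This shows how few subjects carry the comparison. It does not estimate how many results would change.

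**The case against.** **The device limits the operator.** The robot searches for the signal, Valsalva timing is prescribed with an objective adequacy check, and completeness is judged afterwards against a definition. This largely stands. A reader might infer that the NB-IS operator controls signal selection, injection, Valsalva timing and completeness of the session. The documents do not support that. No section gives injection to this operator, and section 6.12.3 speaks of the person injecting without equating the two roles. What remains is narrower: set-up, registration, gel, coaching and repeat attempts.

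**The rule sits where local reading happens.** Local shunt grades are collected for SOC TCD only, and section 6.12.4 lists no local result for NB-IS. This is a plausible reason for the wording, but the protocol does not state it, and it does not address acquisition.

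**TCD may be shorthand for both exams, or one person may run both.** Section 6.12.2 names NB-IS and SOC TCD together when it means both, whereas the blinding sentence names SOC TCD alone. No section requires the same operator for both exams, and neither reading helps a subject who has no SOC TCD.

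**The endpoint reads are blinded.** This stands in full for interpretation.

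**A loss of power.** A reader might want to express the gap as a change in power by assuming some shift in NB-IS detection. The documents give no such shift, and the worry is a biased difference in sensitivity, which power does not measure.

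**Conclusion.** The gap is real and its mechanism is limited. The only operator-blinding rule omits the operator of the index test, the permitted order of tests lets the TTE result be known beforehand, and core-laboratory blinding does not reach acquisition. Knowledge of TTE could therefore affect NB-IS detection or evaluability.

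Neither size nor direction can be derived. The documents do not give the share of subjects with TTE first, the share without SOC TCD, or how far acquisition depends on the operator. They do not support a reading that the primary result will be biased, or biased in favour of NB-IS.

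The conclusion assumes that the user manual and the investigators' training modules, which are not part of these documents, contain no blinding rule of their own. The change should be made because it is cheap and the problem cannot be corrected after data collection. It does not undermine the design as a whole.

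**What to change.** 1. Extend the sentence in section 6.12: the NB-IS operator, and where feasible the person injecting contrast, is also to be unaware of any earlier TTE or TEE result until the NB-IS session ends.
2. Add one eCRF item recording whether this was met.
3. Prespecify a sensitivity analysis that repeats the primary analysis without unblinded sessions. Test order is already known from the dates and times collected under sections 6.12.4 to 6.12.6, so sessions where NB-IS came first can be identified without new data.

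The injector should not be required to be unaware of the SOC TCD result. Section 6.12.3 prefers SOC TCD before NB-IS in the same session with the same injector, and such a rule would conflict with it.

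The cost is one sentence, one eCRF item, one extra analysis and some burden at sites in keeping TTE and TEE results from the scanning staff. The sensitivity analysis will have fewer subjects and so less precision. No test, visit schedule or sample size changes.
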